6	7 April	We added abnormal serum lipids as an exclusion criterion (section 12.0, page 26). We added an additional questionnaire at baseline to evaluate vitamin D status as a baseline health outcome and a study exit survey at study conclusion (Table 1 and section 8.2). We clarified that we will also measure iodine concentration in the urine samples to help interpret thyroid and other hormone concentrations at baseline and study end. We would also like to increase our potential sample size to 40 from 32 to account for a possibility of drop outs and ensure we have a complete sample of 32 participants; we still plan on recruiting as close to half men and half women as possible with a balance between our two intervention groups. We also added an exit survey. We uploaded the Vitamin D Food Frequency and Lifestyle Questionnaire and the Exit Survey.	Yes

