## 1.0 Study Summary

Study Title	Exploring the Role of Peanuts in Enhancing Healthy Weight Gain in Athletic Individuals
Study Design	Randomly Assigned Intervention Study
Primary Objective	Determine the efficacy of the standard hypercaloric sports performance diet (500 kcal surplus energy, adequate protein and carbohydrate, judicious fat) and weight training regimen with excess calories from peanut foods or high-carbohydrate snack foods on weight and lean mass gains over 10 weeks in athletic men and women desiring weight gain.
Secondary Objective(s)	Secondary Aim: Evaluate the ease and acceptability of whole peanuts, peanut butter and peanut-based healthy snacks relative to high-carbohydrate snacks as part of the standard hypercaloric regimen. Exploratory Aim: Examine the effect of potential adaptive factors (increased resting metabolism, decreased appetite) and individual characteristics (sex, age, training history, somatotype) on weight and lean mass gains.
Study Population	Athletic and military men and women who desire weight gain primarily as lean mass to improve performance and/or effectiveness in sport/military endeavors.
Sample Size	32 (16 men and 16 women)
Research Intervention(s)/ Investigational Agent(s)	Men and women will be randomly assigned to a peanut intervention or control group (8 men and 8 women per group); Each group will undergo a 10-wk diet and weight training regimen designed to promote healthy weight gain.
Study Duration for Individual Participants	12 to 13 weeks including screening, baseline testing, the 10-week intervention and post-testing
Acronyms and Definitions	DXA, Dual-Energy X-ray Absorptiometry; TSH, thyroid-stimulating hormone; CBC, complete blood count; RMR, resting metabolic rate; REE, resting energy expenditure; VO 2 max, maximal oxygen uptake during exercise, also known as aerobic capacity; Reps; repetitions; CGM, continuous glucose monitoring; ISAK, International Standards for Anthropometric Assessment; ACSM, American College of Sports Medicine; IUSCA, International Universities Strength and Conditioning Association; HIP Laboratory, Human Integrated Physiology Laboratory; NEM Laboratory, Nutrition and Exercise Metabolism Laboratory

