### Secondary Endpoints

- Change in Resting Metabolic Rate/Resting Energy Expenditure
- Change in Hormone and Metabolic Markers in Blood including testosterone (free & total), growth hormone, insulin-like growth factor, leptin, insulin, thyroid hormones, cortisol and ghrelin and urinary creatinine and urinary iodine
- Change in Strength (all muscle groups)
- Change in Aerobic Fitness
- Change in Walking Economy

Change in and absolute values of Health Outcomes (blood pressure, serum cholesterol, fasting and 24-hour glucose concentration, and hydration status)

Change in Dietary Patterns

Change in Physical Activity and Structured Exercise

Change in Appetite

Baseline vitamin D intake and status and change in serum vitamin D

**4.2** *Describe any primary or secondary safety endpoints. These should be included for all studies that are greater than minimal risk. (Minimal risk: The probability and magnitude of harm or discomfort anticipated in the research that are not greater in and of themselves than those ordinarily encountered in daily life or during the performance of routine physical or psychological examinations or tests.):*

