**Resistance Training.** Participants will undergo rigorous resistance training three days/week in the NEM laboratory under close supervision. The following will be performed with weight machines (Nautilus) and free weights: leg press, squat, leg extension, leg flexion, toe raise, lat-pull down, dead lift, shoulder press, bench press, bicep curl, triceps extension and abdominal twist/crunch. The overall goal will be to have participants perform 10 sets of exercises that work the major muscle groups each week in accordance with a recently published position stand of the International Universities Strength and Conditioning Association (IUSCA) (Schoenfeld et al 2021) with slightly different set of exercises performed on each of the three days. Participants will begin with light to moderate resistance for 8-15 repetitions, after which resistance will be gradually increased in the next 5 workouts. After that, three to five sets of each exercise will be completed using modified methodology of Bartels et al (Kreider, Klesges et al. 1996) (previously shown to effectively promote weight gain) in accordance with the latest

guidelines for promoting muscle hypertrophy (Schoenfeld et al 2021). . Resistance will be adjusted upward after 8 repetitions are fully executed using proper technique. Participants engaged in a sport or military training activity will be instructed to maintain their normal training throughout the study.

Table 1. Overview of Data Collection

Overview of Data Collection	Baseline	3 wk	7 wk	11 wk
Body Mass (weight)	x	x	x	x
Body Composition by DXA and spot urine sample; Pregnancy test by urine in female participants	x	x	x	x
Skinfolds & circumferences	x			x
Resting metabolic rate-RMR	x	x		x
Blood via venipuncture and Urine vis 24-hr collection				
CBC and TSH	x			
Testosterone (free &total)	x	x	x	x
Growth Hormone	x	x	x	x
Insulin-like growth factor	x	x	x	x
Leptin	x	x	x	x
Insulin	x	x	x	x
Free T4	x	x	x	x
Cortisol	x			x
Ghrelin	x	x	x	x
Urinary creatinine and urinary iodine	x			x
Health outcomes				
Blood Pressure	x	x	x	x
Serum Lipids	x			x
Serum Vitamin D	x			x
Fasting blood glucose	x			x
Continuous glucose monitoring	x			x
Compliance and Fitness Testing				

Strength Testing	x			x
Aerobic Capacity (VO2max) and walking efficiency	x			x
Food Records and Appetite rating for 3-day	x	x	x	x
Vitamin D Food Frequency and Lifestyle Questionnaire	x			
Exercise tracking for 3-days (smart watch)	x	x	x	x
Daily snack tracking logs and exercise logs	↔	↔	↔	→

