**Dietary food records, exercise tracking, continuous glucose monitoring (CGM), and 24-hour urine collection:** Following laboratory testing, participants will be instructed on completing 3-day food records and exercise tracking, performing the CGM and completing the 24-hour urine collection. Participants will be asked to record all of the food they eat for 3 days, rate feelings of hunger and appetite using standardized appetite rating sheets, and wear a smart watch over this same time period. At baseline only, they will be asked to complete a food-frequency and lifestyle questionnaire specific to vitamin D intake/status simultaneously with the 3-day food records. The smart watch will use an app to measure heart rate and estimate energy expended during structured exercise or physical activity; this will be used to help estimate the participants total energy expenditure. It will be necessary to have the GPS function turned on during the collection of physical activity data but only data related to time, distance or intensity and not GPS coordinates will be downloaded or recorded. CGM will also coincide with the three-day food records using a device called a “Continuous Glucose Monitor” that is typically worn on the back of the upper arm. This requires that a small amount of interstitial fluid (0.5 microliters) be sampled every 15 minutes (96 times per day) throughout the course of the 3-day measurement. In addition, participants will be asked to collect urine for 24 hours during one day of this recall or within the first week of the study. Participants will void and discard the first morning urine sample and then collect all subsequent samples in provided clinical urine jugs for 24 hours, ending with the first sample upon waking the next day. Participants will schedule a time to drop off their urine during one of their resistant training sessions the first week or at a separate time, if it is more convenient. The instructions the participants will receive on using the Smart Watch, using CGM, and collecting the 24-hour urine are uploaded as an Addendum.

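### The baseline 24-hour urine may be collected in the first training week, so for some participants it may not be a pre-intervention value

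*Combined protocol and SAP*

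**What the plan says.** Section 8.2, under the baseline laboratory testing session, sets the timing of the first 24-hour urine: "participants will be asked to collect urine for 24 hours during one day of this recall or within the first week of the study". The recall meant there is the 3-day food record kept after the baseline laboratory visit. For returning the sample, participants may "drop off their urine during one of their resistant training sessions the first week or at a separate time", whichever is easier for them.

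Four other places bear on this:

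- **Table 1 (Section 8.1)** marks the row "Urinary creatinine and urinary iodine" at Baseline and 11 wk, and at no visit between.
- **Section 4.1** names change in a list of blood and urine markers as a secondary endpoint; the list ends with "urinary creatinine and urinary iodine".
- **Revision History, entry 6**, gives the purpose of the iodine assay: to "measure iodine concentration in the urine samples to help interpret thyroid and other hormone concentrations at baseline and study end".
- **Section 1.0** describes diet and training as one regimen: "Each group will undergo a 10-wk diet and weight training regimen designed to promote healthy weight gain".

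Participants are randomised after consent (Section 8.1) and are told whether they are in the peanut or the non-peanut group (Section 8.2, Dietary Intervention).

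**The concern.** A baseline for a change endpoint should be taken before anything the trial does to the participant. The first window meets that; the second does not guarantee it. With only two scheduled values per participant, no later measurement can stand in for a compromised first one.

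Two things are at stake. First, the change in urinary creatinine and iodine could mix participants whose starting value precedes the intervention with others whose starting value falls within it. The participant's choice of window comes after randomisation and may be made with knowledge of group, so nothing ensures that the mix is the same in both arms. Second, iodine is supposed to inform the reading of baseline hormones. Those bloods are drawn at the screening visit or the baseline laboratory session, before the intervention, so a week-1 urine would describe a different period.

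**Working it through.** The plan states no figure on this point, so there is none to reproduce. The check is a comparison of texts, then bounds on exposure.

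**1. Which week is meant.** Section 8.2 joins the two windows with *or*, so the second is separate from the food-record days. The phrase about the first week of the study is not defined. The return instruction refers to training sessions in the first week, and supervised training is part of the intervention. Intervention week 1 is therefore the more natural reading.

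**2. Whether another rule closes the gap.** Nothing in Sections 4.1, 5.2, 8.1 or 8.2 requires the collection to be finished before the first snack or session, requires its timing relative to intervention start to be recorded, or says how late samples are analysed. The 36-hour limit on heavy exercise in Section 8.2 is stated for the laboratory measurements, not for the 24-hour urine.

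**3. Upper bound on exposure for a late collector.** Inputs: 10 weeks and 3 sessions per week (Sections 1.0 and 8.2); 500 kcal of snacks per day, with 15 g protein in the peanut arm and about 5 g in the control arm (Section 8.2).

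- Sessions: 3 of 3 × 10 = 30, or 10%. If the sample is returned at a week-1 session, collection has already ended, so at most 2 of 30 (6.7%) precede it. Three requires collection at the very end of the week and return at a separate time.
- Snack days: 7 of 7 × 10 = 70, or 10%, counting the collection day itself.
- Surplus energy: 7 × 500 = 3,500 of 70 × 500 = 35,000 kcal.
- Snack protein: 7 × 15 = 105 g (peanut) against 7 × 5 = 35 g (control), a gap of 15 − 5 = 10 g per day.

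These are shares of exposure, not of bias.

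**4. Illustration of the effect on the change.** Let *p* be the share of participants who collect late and *s* the fraction of the week-11 change already present in a late sample. Then

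observed mean change ÷ true mean change = 1 − *p* × *s*.

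The documents give neither quantity. With assumed values:

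| *p* | *s* | observed ÷ true |
|---|---|---|
| 0 | any | 1 |
| 0.25 | 0.10 | 0.975 |
| 0.50 | 0.25 | 0.875 |
| 1.00 | 0.50 | 0.50 |

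If both arms truly change by the same amount but late shares are 25% and 75%, the spurious difference between arms is (0.75 − 0.25) × *s* of that change: 5% at *s* = 0.10 and 25% at *s* = 0.50. With equal late shares it is zero. An early response need not point the same way as the week-11 response, so *s* could also be negative; the direction is not fixed.

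**The case against.** The strongest reply is that the text permits a late collection but does not call for one. The food-record window is listed first, and returning urine at a training session does not show that it was collected after training began. The first week of the study could be read as the baseline week, since participation runs 12 to 13 weeks including screening and baseline (Section 11.1). The participant instructions for the urine are in an addendum that is not part of the documents, and may fix the day. Participants must already be resistance trained with adequate protein intake (Section 12.2), training starts light to moderate, and the snack protein differs by only about 10 g per day, so a few days may move creatinine little.

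All of this limits the size of the problem, and it is why no bias can be quantified. It does not remove the permission itself, which the protocol text states.

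Two stronger readings should not be drawn. A reader might infer that adjusting for this baseline would remove part of the snack effect; Section 5.2 plans no adjustment for a urinary baseline, so that harm belongs to an analysis nobody has proposed. A reader might also infer that most of any snack-related iodine change would already be present by week 1; the documents do not give the iodine content of either arm's snacks, so there is no basis for that.

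**Conclusion.** The point stands as a minor one. The protocol allows a sample labelled Baseline to be taken during the intervention, and that sample is the only starting value for two secondary markers. For anyone using the later window after a first snack or session, the recorded change may not start from a pre-intervention value, and the iodine result may be paired with earlier bloods.

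Exposure before or during a late sample is at most about 10% of the regimen. Whether that produces a bias, how large, and in which direction cannot be derived from the documents; the attenuation figures are illustrations on assumed inputs, and with no late collection the bias is zero. The conclusion rests on reading the first week as intervention week 1 and on the unseen addendum not already fixing the day. Body weight, DXA measures and the other primary outcomes are unaffected, as are the baseline bloods.

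**What to change.** In Section 8.2, replace the two windows with one: the baseline 24-hour urine is collected during one day of the baseline 3-day food record and completed before the first study snack and the first training session. Return of the container at the first training session can stay, which keeps most of the convenience. Bring the participant instruction sheet into line if it differs.

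Record the date of collection relative to the start of the intervention, and add to Section 5.2 that any late sample is flagged and that the change in urinary creatinine and iodine is repeated without late samples as a sensitivity analysis.

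The cost is a sentence in each section, one date field, and slightly less scheduling flexibility before training starts.

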### Healthy Weight Gain Intervention

**Resistance Training:** Participants will undergo rigorous resistance training three days per wk under close supervision. The following will be performed with weight

machines (Nautilus) and free weights: leg press, leg squat, leg extension, leg flexion, toe raise, lat-pull down, dead lift, shoulder press, bench press, bicep curl, triceps extension and abdominal twist/crunch. The overall goal will be to have participants perform 10 sets of exercises that work the major muscle groups each week in accordance with a recently published position stand of the International Universities Strength and Conditioning Association (IUSCA) (Schoenfeld et al 2021) with slightly different set of exercises performed on each of the three days. Participants will begin with light to moderate resistance for ~8-15 repetitions, after which resistance will be gradually increased over the following 5 workouts. After that, three to five sets of each exercise will be completed using modified methodology of Bartels et al in accordance with the latest guidelines for promoting muscle hypertrophy (Schoenfeld et al 2021). The resistance training sessions will last approximately 60 to 75 minutes.

**Dietary Intervention:** The peanut group will be provided with a variety of whole and laboratory-prepared peanut-containing snacks to meet their daily excess energy. The snacks will be calculated to contain 500+- 10 kcal and 15 grams of protein (using Nutrition Data System for Research nutrient analysis software). A complete list of these snacks is uploaded as supplemental files. The control group will be provided similar 500 kcal high carbohydrate containing snacks that contain ~5 g protein.. Participants will be informed that they are in the peanut or non-peanut group but the dietary composition differences between these snacks will not be mentioned or discussed. Participants will be encouraged to consume snacks within an hour of resistance training and/or before bed (Phillips and Van Loon 2011). Participants in both groups will be allowed to select from several different snack options offered each week. Participants will also undergo weekly assessments during one of the resistance training sessions to ensure compliance and adequate progress with excess energy adjusted upward with weight gain to avoid the potential effects of acute energy imbalance due to total body/lean mass gain and help ensure adequate (~0.5 pounds/week) but not excessive (>1.5 #/week) weight gain.

**Daily Snack and Exercise Tracking Logs:** Participants will keep daily record of consumption of the provided snacks as well as other exercise training undertaken using a simple snack and exercise tracking log. These logs require participants to place a check mark by snacks consumed and to quickly fill in time spent in other exercise training activities. Logs will be turned in to the researchers every two weeks during resistance training sessions.

**Strength and Fitness Testing:** Strength of a major upper and lower body group (i.e. bench press and leg press) will be assessed on the Nautilus equipment at the beginning and end (wk 11) of the 10-wk program by recording the maximal weight that can be lifted once correctly. The change in the aforementioned 80% RM value will also be documented for use as data points.

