### 2.2 *State the hypotheses to be tested:*

The standard hypercaloric sports performance diet (500 kcal surplus energy, adequate protein and carbohydrate, judicious fat) and resistance training regimen with excess calories from peanut foods or high-carbohydrate snack foods will result in an average weight gain of 1/2 pound/week in both men and women, with the majority of that gain as lean (fat-free mass) mass.

Weight gain will be more efficient when the excess calories are from peanut foods (compared to control, high-carbohydrate foods) which will be better accepted than the control snacks.

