## 8.0 Procedures Involved

### 8.1 Describe and explain the study design:

Sixteen men and sixteen women between the ages of 18 and 40 will be randomly assigned to the peanut intervention or control group (8 men/8 women/group). A computer program with a random number generator will be used by the study coordinator to assign male participants and female participants to the peanut or control group (i.e., each sex will be separately randomized).

As outlined in the table, eligible participants will undergo a 10-wk diet and training regimen designed to promote healthy weight gain. This will include increasing energy intake by 500 additional kcal/day (above their typical weight maintenance diet and accounting for energy requirements of resistance training) through provision of peanut-based whole foods/snacks or high-carbohydrate containing control snacks along

with a supervised rigorous resistance training regimen designed to promote muscle hypertrophy. After providing informed consent, participants will be randomly assigned to the peanut or control group based on sex. Outcome data will include assessment of body mass, total and regional body composition via DXA and body anthropometrics, skinfolds and somatotyping using the International Standards for Anthropometric Assessment (ISAK) (Stewart, Marfell-Jones et al. 2011) along with measures of resting metabolic rate (RMR), circulating hormones and serum/plasma biomarkers. The latter includes measurement of potentially important hormones/ biomarkers of anabolism, stress, overfeeding, and cardiometabolic health. Compliance to the nutrition and exercise regimen will be evaluated at regular intervals and include collection of 3-day food records (performed at baseline and 3-days prior to each assessment point) and physical activity data collected by digital technology (Garmin Vena SQ smart watch and My PT Hub app).

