## **16.0 Withdrawal of Subjects**

*16.1 Describe circumstances under which you anticipate subjects could be withdrawn from the research without their consent:*

Participants could be withdrawn from the study if they are not showing up for appointments and/or training sessions, are not consuming the provided snacks, or are not completing or complying with all procedures. They also may be withdrawn if they develop an injury or illness that would prevent

them from doing everything that is expected for the study or which might compromise their health.

*16.2 If applicable, describe any procedures for orderly termination (e.g., discontinuation of a study drug or debriefing after a behavioral intervention):*

If a participant is not complying with the study, the PI or study coordinator will first discuss these difficulties with the participant and explain the importance of adhering to the intervention for the purpose of the study. If it is determined that the participant be terminated or discontinued from the study for reasons as described above, the PI will mitigate issues leading to these problems. The participant will be provided any information which is available to them (baseline body composition, fitness testing, resting metabolic rate). It will then be suggested that the study personnel part ways with the participant

*16.3 Describe procedures that you will follow when subjects withdraw from the research, including partial withdrawal from procedures with continued data collection (e.g., participant declines to continue with regular blood draws, but continues with periodic behavioral questionnaires):*

Any participant can discontinue participation at any point without consequence.

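### The daily snack log, as described, cannot show how much of a snack was eaten, so a difference in intake between arms could be mistaken for a difference in gain per calorie

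*Combined protocol and SAP*

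**What the plan says.** **The log.** Section 8.2 (Daily Snack and Exercise Tracking Logs) states: "These logs require participants to place a check mark by snacks consumed". It adds: "Logs will be turned in to the researchers every two weeks during resistance training sessions". No field for quantity and no handling of leftovers is described. Table 1 lists the log under compliance and fitness testing.

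**The snacks.** For the peanut arm, section 8.2 says: "The snacks will be calculated to contain 500+- 10 kcal and 15 grams of protein". For the other arm: "The control group will be provided similar 500 kcal high carbohydrate containing snacks that contain ~5 g protein". The weekly assessments come with "excess energy adjusted upward with weight gain", so the amount provided may change during the trial.

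**Other intake data.** Section 8.1 and Table 1 schedule 3-day food records at baseline and before the 3-, 7- and 11-week assessments. Section 8.2 says that these cover all food eaten. Energy intake and its change are listed among the primary endpoints in section 4.1. Weekly compliance assessments are planned, but their method is not described.

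**The claim.** Section 2.2 states: "Weight gain will be more efficient when the excess calories are from peanut foods". The same sentence predicts that peanut foods will be better accepted than the control snacks. Efficiency is not defined.

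**The analysis.** Section 5.2 compares body weight, body composition and anthropometry by group and over time with repeated measures ANOVA. It gives no role to energy intake, the snack log or the food records.

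**The concern.** A claim about gain per calorie needs the calories eaten. Someone who eats half a snack must either tick it or leave it blank, and neither is right. The described log also does not say how large the snack was.

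This would matter little if the arms could be expected to eat alike. The protocol predicts that they will not like the snacks equally. If control snacks are left unfinished more often, controls receive a smaller surplus and may gain less for that reason alone. Read against section 2.2, the smaller gain could pass for evidence that peanut calories work better, and the daily record could not show otherwise.

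What is at stake is the efficiency hypothesis, not the randomised comparison of the two regimens as assigned.

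**Working it through.** The protocol gives no power calculation, effect size, standard deviation or expected rate of partial eating, so there is no stated figure to reproduce. The arithmetic below is an illustration.

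**Inputs from the protocol:** 500 kcal/day of snacks; 10 weeks = 70 days; hypothesised gain 0.5 lb/week (section 2.2), so 5 lb = 2.27 kg; background tissue cost of about 5 kcal/g (section 3.1); 16 per arm (section 1.0).

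**Assumed:** fractions eaten of 95% (peanut) and 80% (control); a constant 500 kcal/day provided; gain proportional to snack energy eaten; no compensation from other food; SD of weight change 1 to 2 kg.

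**1. Coverage of the food records**
- Three on-treatment records × 3 days = 9 days; 9/70 = 12.9%.
- If the week-11 record falls after the 10 weeks: 6/70 = 8.6%.

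**2. Intake gap**
- (0.95 − 0.80) × 500 = 75 kcal/day; × 70 = 5,250 kcal.

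**3. Gap in gain, pro rata to the hypothesised gain**
- Full intake: 500 × 70 = 35,000 kcal, taken to give 5 lb.
- Peanut: 0.95 × 5 = 4.75 lb. Control: 0.80 × 5 = 4.00 lb. Difference: 0.75 lb = 0.34 kg.

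**4. What the efficiency claim would show**
- Per kcal provided: (4.75/35,000) ÷ (4.00/35,000) = 1.19, so peanut calories look 19% more efficient.
- Per kcal eaten: 4.75/33,250 = 4.00/28,000 = 0.143 lb per 1,000 kcal, so there is no difference. The apparent advantage comes wholly from the unrecorded leftovers.

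**5. Check of the conversion scale**
- 5 kcal/g applied to full intake: 35,000/5 = 7,000 g = 15.4 lb.
- An assumed 3,500 kcal/lb: 35,000/3,500 = 10 lb.
- Neither gives the hypothesised 5 lb. Converting the gap on one of these scales (5,250 kcal = 2.3 lb or 1.5 lb) and setting it against 5 lb would mix scales. Pro rata is the consistent choice: a 15-point gap is 15% of the full-intake gain.

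**6. Range of gaps (assumed), pro rata**

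| Gap in fraction eaten | kcal/day | lb | kg |
|---|---|---|---|
| 5 points | 25 | 0.25 | 0.11 |
| 10 points | 50 | 0.50 | 0.23 |
| 15 points | 75 | 0.75 | 0.34 |
| 20 points | 100 | 1.00 | 0.45 |
| 30 points | 150 | 1.50 | 0.68 |

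**7. Would the gap alone reach p < 0.05?** (taking the test as two-sided, 16 per arm)
- Difference detectable with 80% power: (1.96 + 0.84) × √(2/16) = 0.99 SD (1.02 SD by t-test).
- Probability = Φ(d/(SD × √(2/16)) − 1.96). For d = 0.34 kg: SD 1 kg, Φ(0.96 − 1.96) = 0.16; SD 2 kg, Φ(0.48 − 1.96) = 0.07.
- For a 20-point gap (0.45 kg) the corresponding figures are 0.25 and 0.09.

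Unequal eating of this size would seldom be significant by itself. It would bias the estimate, by an amount that the daily log cannot reveal.

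**The case against.** **Intake is measured elsewhere.** Energy intake is a listed endpoint, the food records cover all food on their days, and compliance is assessed weekly. A large difference between arms would have somewhere to appear. This stands, and it rules out saying that unequal eating would go unseen. But the records are self-reported and cover few days, the weekly method is not described, and neither measure is linked to the weight analysis.

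**Unequal eating is part of the regimen.** If control snacks are less palatable and therefore less eaten, that is a real consequence of assigning them, and the second aim studies acceptability. This also stands. It protects the comparison by assigned group, but not a statement about calories.

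**The form may hold more than the text.** Section 8.4 says that most collection sheets are uploaded separately, so an amount field cannot be excluded. Section 8.2 nevertheless describes only a tick.

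**Stronger readings that the text does not support.** A reader might infer that each tick is credited as 500 kcal; no such rule is stated, and one tick may cover only part of a day's provision. A reader might also infer that the weekly check, or withdrawal of people who "are not consuming the provided snacks", rests on the log. Neither is tied to it, and logs handed in fortnightly cannot alone serve a weekly check.

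**Conclusion.** The point holds as a limitation of measurement and interpretation. The described log cannot show partial intake or the amount provided, quantified intake covers at most 9 of 70 days, and the weight analysis does not use it. A difference in the amount eaten could therefore be mistaken for a difference in gain per calorie. A reader might conclude that the trial's group comparison is invalid, but it remains a sound comparison of the assigned snack regimens.

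The illustrative size is 0.75 lb (0.34 kg) of the hypothesised 5 lb, for 95% versus 80% eaten, and 0.25 lb (0.11 kg) for a 5-point gap. These rest on assumed fractions, proportional gain and no compensation from other food. The documents support the mechanism but give no estimate of its size. This is a worthwhile, cheap improvement.

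**What to change.** - Replace the tick with two entries per snack: the amount provided that day, and the fraction eaten (none, 1/4, 1/2, 3/4, all).
- Report snack kcal eaten per day by arm beside the weight and lean-mass results.
- State in section 5.2 that the comparison by assigned group is the main analysis, and that any statement about efficiency rests on gain per kcal of snack eaten, as a supportive analysis. Intake is observed after randomisation, so this second comparison is not protected by it.

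**Cost:** a revised log page, one descriptive table, a few lines in section 5.2 and slightly more effort for participants each day. The record remains self-reported. Returning leftovers or containers would add a check, but it also adds burden and is not needed for this fix.
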